#### **Research questions for Part A – ‘Perception of self-paced performance variations’**

- Do PwMS with and without reported fatigue, and HC differ in their perceptive accuracy for detecting walking speed variations and STS duration variations during self-paced experimental protocols? Are these difference modulated by the accumulation of fatigue during the course of the protocol?
- Do PwMS with and without reported fatigue, and HC differ in their perceptive accuracy for detecting gait smoothness and STS smoothness variations during self-paced experimental protocols? Are these difference modulated by the accumulation of fatigue during the course of the protocol?

- Do PwMS and HC differ in the correspondence between measured and subjective (i.e. confidence rating) dimensions of perceptive accuracy?

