# Assessment of perceptive accuracy for motor performance in persons with multiple sclerosis

## Introduction

The majority of people with multiple sclerosis (PwMS) have impaired gait and sit-to-stand function: they walk slower, with an increased energetic cost of walking and cluster-specific alterations from the physiological gait pattern, while lower limb extensor weakness and diminished postural control have also an impact on their sit-to-stand performance. (1-4)

After sustained activity these impairments tend to increase for a large part of PwMS: motor performance fatigability, the objectively measured acute performance deterioration, may involve both quantitative and qualitative aspects of their motor performance. (5, 6)

This can be a barrier to participation in leisure-time physical activity (PA), creating a vicious circle leading to increase in disability: inactive PwMS walk slower with an increased energetic cost of walking, consequently experiencing more reductions in walking bouts quality and distance in their daily life.

Furthermore, motor performance impairments and levels of PA, in this population, may also be linked to sensory abnormalities, personal beliefs and fluctuations of symptom intensity. (7-11)

Fatigue is the hallmark symptom in MS, with reported prevalence reaching 78%, and PwMS with higher levels of perceived fatigue tend to become less physically active in their daily life, also in absence of motor performance fatigability. (12, 13)

Generally, fatigue is a sense of tiredness and lack of energy that can interfere with a person's usual daily activities and, leading to increase the weighting of effort costs in cost-benefit evaluations, it can be a functional interoceptive signal to stop or modify our activity, take appropriate rests or pace our efforts. (14)

[figure not shown]

Figure 1 The predictive model of bodily states. Illustration of the interoceptive core control network and of the precision weighted inferential process forming perception. Adapted from (15)

The efficiency of this self-regulation system depends on the ability of the central interoceptive core control network to accurately judge our body state (which resources are available versus necessary to achieve a desired outcome) and, when carrying out physical activity, to timely produce allostasis adjustments (i.e. 'actions to maintain the body in homeostasis') through interactions with the

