### **Research questions for Part B – ‘Perception of imposed performance variations’**

- Do PwMS with and without reported fatigue, and HC differ in their perceptive accuracy for imposed walking speed variations during treadmill-based experimental protocols? Are these difference modulated by the accumulation of fatigue during the course of the protocol?
- Do PwMS with and without reported fatigue, and HC differ in their perceptive accuracy for imposed STS vertical excursion variations during self-paced experimental protocols? Are these difference modulated by the accumulation of fatigue during the course of the protocol?
- Are these difference modulated by time (different subphases) within the course of the protocol?
- Do PwMS and HC differ in the correspondence between measured and subjective (i.e. confidence rating) dimensions of perceptive accuracy?

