### **Hypothesis**

- PwMS and HC will differ in the measured outcomes of perceptive accuracy for imposed walking speed variations during treadmill-based experimental protocols, lower accuracy is expected in PwMS with higher reported fatigue
- PwMS and HC will differ in the measured outcomes of perceptive accuracy for imposed STS vertical excursion variations during self-paced experimental protocols, lower accuracy is expected in PwMS with higher reported fatigue
- PwMS will be less accurate than controls to a larger extend in the last subphase of the protocol (i.e. returning to comfortable speed or seat height levels from the most difficult performance level)
- Lower correspondence between measured and subjective (i.e. confidence rating) dimensions of perceptive accuracy is expected in PwMS

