## Data and statistical analysis

Motor performance data (gait and STS kinematic, kinetics and spatial-temporal parameters) will be acquired by wearable sensors and extracted from Moveo software (APDM) as .csv file or raw data, and Matlab scripts will be used in case of parameters requiring specific calculation. Data acquired from the participants reports on their perception, during the experimental tasks in Part A and Part B, will be extracted with dedicated Matlab scripts. Statistical analysis will be performed using SPSS (V. 28.01). Tests of normality (Shapiro-Wilk test) will be used to determine if parametric or non-parametric statistical tests have to be used for the comparisons and correlations. The  $\alpha$  for all analyses will be set at 0,05.

**Clinical assessment** outcomes, with a particular focus on the MAIA-2, ISAQ and PAS scores and subscores, will be compared between groups with an independent T test (or with its non-parametric equivalent Mann-Whitney U-Test), to detect significant differences in the subjective beliefs about perceptive abilities.

In the **experimental Part A** we will obtain the participants' minimal perceptive threshold for self-paced performance variations which will be compared between groups with an independent T test (or with its non-parametric equivalent). We will also relate the frequency of the reports with the measured performance variability (coefficient of variation of the selected motor performance parameter: gait speed or STS duration) to obtain a novel outcome measure reflecting perceptive accuracy. We will study it between and within groups using a mixed model ANOVA with time and group as factors to detect significant differences between PwMS and controls and its variations relative to the accumulation of fatigue during the prolonged motor tasks. To investigate its interference with perceptive accuracy the difference between the subjective rate of fatigue (VAS-F) pre-post task protocols will be included in the analysis as covariate.

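### Four accuracy questions separate people with MS by reported fatigue, but the planned group tests are written as MS versus controls, with no fatigue split and no named fatigue test

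*Combined protocol and SAP*

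**What the plan says.** **Questions.** Under 'Research questions for Part A', the first two questions name three groups: "Do PwMS with and without reported fatigue, and HC differ in their perceptive accuracy for detecting walking speed variations" (the same question also covers sit-to-stand duration) and "Do PwMS with and without reported fatigue, and HC differ in their perceptive accuracy for detecting gait smoothness and STS smoothness variations". Under 'Research questions for Part B', the first two do the same: "Do PwMS with and without reported fatigue, and HC differ in their perceptive accuracy for imposed walking speed variations during treadmill-based experimental protocols" and "Do PwMS with and without reported fatigue, and HC differ in their perceptive accuracy for imposed STS vertical excursion variations".

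**Hypotheses.** In both parts, the accuracy hypotheses first state that PwMS and HC will differ, then add that "lower accuracy is expected in PwMS with higher reported fatigue".

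**Analysis.** 'Data and statistical analysis' compares the Part A perceptive threshold between groups with an independent t test or its non-parametric equivalent. It studies Part A accuracy "using a mixed model ANOVA with time and group as factors to detect significant differences between PwMS and controls". The Part B model is worded the same way, with protocol subphase as the time factor. In both models the pre-post difference in VAS-F is a covariate.

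**Fatigue data.** 'Questionnaires' lists the FSMC and the MFIS for both groups, without a cut-off. 'Participants' recruits one undivided PwMS group. The analysis section closes with correlations run separately per group between accuracy and demographics, questionnaires and clinical assessments, followed by a regression. No fatigue scale is named there.

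**The concern.** The questions need a comparison among three groups, while the accuracy analyses are written for two. Followed as written, the plan gives a PwMS versus HC contrast for each outcome and no comparison of PwMS with fatigue, PwMS without fatigue, and HC.

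Two things are at stake. First, if lower accuracy is confined to fatigued PwMS, the pooled contrast shrinks in proportion to the fatigued share and may miss the effect. Second, with two fatigue questionnaires and no cut-off, any split made later could be chosen after the data are seen. A within-PwMS fatigue association found among many candidate predictors would also be hard to present as a test of the stated hypothesis.

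**Working it through.** **1. Questions against analyses.**

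| Question | Groups asked about | Planned analysis | Match? |
|---|---|---|---|
| Part A: speed and sit-to-stand duration | three | mixed ANOVA, PwMS and controls; t test on threshold | no |
| Part A: smoothness | three | as above | no |
| Part B: treadmill speed | three | mixed ANOVA, PwMS and controls | no |
| Part B: sit-to-stand excursion | three | mixed ANOVA, PwMS and controls | no |
| Beliefs (MAIA-2, ISAQ, PAS) | two | t test or Mann-Whitney | yes |
| Correspondence with confidence rating | two | t test or equivalent | yes |

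Four questions name three groups. No planned group test contains a fatigue split.

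**2. Does the VAS-F covariate fill the gap?** The protocol describes the VAS-F as a scale for state fatigue, and the models use its change across a task. That serves the second sentence of each question, on accumulation of fatigue during the protocol. It does not say whether a person reports fatigue at entry.

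**3. The plan's own sample size.** 40 × 1.10 = 44 per group, which matches the protocol. No effect size, SD or power is given for the 40, so the base itself cannot be reproduced.

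**4. Precision of a split.** Inputs: 40 analysable PwMS ('Participants') and an assumed split. The only prevalence in the documents is in the Introduction ("with reported prevalence reaching 78" per cent), an upper literature value and not a planning figure. 0.78 × 40 = 31.2, so about 31/9. An even split is the other illustration. In SD units, SE = √(1/n₁ + 1/n₂):
- 20/20: √(1/20 + 1/20) = 0.316
- 31/9: √(1/31 + 1/9) = 0.379
- Pooled PwMS versus HC, 40/40: √(1/40 + 1/40) = 0.224

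The smallest difference detectable with 80% power (two-sided t test, alpha 0.05; power and sidedness assumed) is 0.63 SD for 40/40, 0.91 SD for 20/20 and 1.09 SD for 31/9.

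**5. Dilution.** Assume that fatigued PwMS differ from HC by 0.6 SD, that non-fatigued PwMS do not differ, and that the within-group SD is common. The pooled difference is (fatigued share) × 0.6. Power is from the noncentral t distribution. The Bonferroni column uses alpha 0.05/3 for three pairwise contrasts.

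| Split | Pooled difference | Power, pooled v HC | Power, fatigued v HC | Same, Bonferroni | Power, fatigued v non-fatigued |
|---|---|---|---|---|---|
| 31/9 | 31/40 × 0.6 = 0.47 SD | 54% | 70% | 52% | 34% |
| 24/16 | 24/40 × 0.6 = 0.36 SD | 36% | 63% | 45% | 44% |
| 20/20 | 20/40 × 0.6 = 0.30 SD | 26% | 58% | 40% | 46% |

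Unadjusted, fatigued versus HC beats the pooled test at every split. After adjustment the advantage disappears at 31/9 (52% against 54%) and remains at the more even splits. The direct contrast of the two PwMS subgroups stays below 50% throughout.

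**The case against.** **The pooled contrast is a stated target.** The aim at the end of the Introduction is to characterise PwMS compared with controls, and each accuracy hypothesis begins with that difference. This stands: pooled PwMS versus HC should remain.

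**The fatigue hypothesis already has a route to analysis.** It is worded as a gradient, and the closing correlations and regression can relate FSMC or MFIS to accuracy within PwMS. This stands in part. A reader might infer that the fatigue hypothesis is never examined, and the documents do not support that. But the analysis is called exploratory and names no fatigue scale. Because it runs separately per group, it cannot compare either PwMS subgroup with HC.

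**The group factor might have three levels.** The number of levels is not stated, so this may be incomplete specification and not a decision to pool. However, both ANOVA sentences name only PwMS and controls, and a t test holds only two groups. If three levels were intended, the scale, cut-off and contrasts are still missing. It is also arguable whether the threshold belongs to the accuracy questions, since the Task 1 description of Part A lists it separately from the ratio that reflects accuracy. The ANOVAs carry the point without it.

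**Not every group test is affected.** A reader might infer that all the planned PwMS versus HC tests are misdirected. They are not: the belief and correspondence questions ask about two groups and have two-group tests.

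**The study is exploratory and the data are safe.** 'Experiment outline' calls it exploratory, and the fatigue scales are collected regardless. This lowers the severity. It does not remove the mismatch, since the plan states directional hypotheses and an alpha of 0.05.

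**Conclusion.** The point holds in a limited form. Four accuracy questions ask for a three-group comparison that no planned analysis makes, and the associated fatigue hypothesis has only an unnamed exploratory analysis. It should be fixed before analysis, but it does not undermine data collection or the pooled comparison.

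The mismatch rests on the text alone. The sizes rest on assumptions: the splits, the 0.6 SD effect, a common SD, two-sided testing and 80% power. The true fatigued share in a sample able to walk six minutes unaided is not given.

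A reader might also infer that splitting PwMS would show whether a difference is due to fatigue or to MS. It would not. This is an observational comparison, and the subgroups may also differ in depression, sleep, pain or disability. A split shows association with fatigue only. Nor do the calculations show that a three-level test is clearly better than pooling once three contrasts are adjusted for, which is why the continuous slope should lead.

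**What to change.** In 'Data and statistical analysis':

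1. Keep pooled PwMS versus HC as the overall contrast in both parts.
2. Name one already collected fatigue scale, FSMC or MFIS, before analysis. The documents give no basis for preferring either. State that its continuous slope on accuracy within PwMS is the test of the fatigue hypothesis, separate from the exploratory predictor screen.
3. Then choose one of two routes:
   - Add a three-level group factor (HC, PwMS without reported fatigue, PwMS with it), with the cut-off fixed before analysis and multiplicity-adjusted contrasts, reported as secondary with confidence intervals.
   - Reword the four questions to PwMS versus HC plus the fatigue slope within PwMS.
4. State that the VAS-F change addresses accumulation of fatigue during the task, so that it is not read as the measure of reported fatigue.

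The cost is analysis wording only, with no new data or visits. On the first route, the subgroup contrasts will be imprecise, and the non-fatigued group may prove too small to interpret. In that case the report should give the slope and say that the three-group question could not be answered.

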### **Hypothesis**

- PwMS and HC will differ in the measured outcomes of perceptive accuracy for self-paced walking speed and STS duration variations, lower accuracy is expected in PwMS with higher reported fatigue
- PwMS and HC will differ in the measured outcomes of perceptive accuracy for self-paced gait and STS smoothness variations, lower accuracy is expected in PwMS with higher reported fatigue
- Lower correspondence between measured and subjective (i.e. confidence rating) dimensions of perceptive accuracy is expected in PwMS

## **Experimental design Part B: 'Perception of imposed performance variations'**

### **Task 1: Perceptive accuracy for imposed speed variations during treadmill walking**

On the third day the participants will be tested on the treadmill starting from a familiarization with the range of treadmill speed, personalized accordingly to a subjective and an objective criteria (see above, 'Range of experimentally-induced performance variations – Treadmill walking'). Consequently, the treadmill speed will be quickly returned to comfortable.

Neutral instructions will be provided to the subject before starting the treadmill test by reading the following script: "Start walking when the treadmill moves and try to pay attention to the belt speed, starting at your comfortable level. You should try to maintain your position on the treadmill for the full length of the experiment. Use the lateral bars for hand support in case of brief necessity but release them as soon as you can. We want you to notice, evaluate and report the actual treadmill speed to the experimenter relative to the visual scale on the screen: its starting position on the zero value of the scale represent your comfortable walking speed. Variations in belt speed may occur at any point throughout the experiment, always within your personalized range of speed. Sometimes it is possible that you will not feel any belt speed variation at all. Every 10 seconds you will be asked to communicate the speed level you are perceiving at that point in time, and your report will be recorded".

During the experimental perceptive task the imposed speed will vary from the baseline in an upward/downward fashion with fixed increments (of 0,028m/s) but with randomized time in between every acceleration: the increase in speed will continue for 15 consecutive incremental steps, although never trespassing the participant's maximal speed (derived from their overground performance in first minute of 6MWT, see above), it will stabilize on that value before decreasing toward the baseline speed (with the same number of consecutive steps). As demonstrated in the example, in figure 5, this protocol will last 6 minutes and will impose the absolute magnitude of speed changes (0,42 m/s) for all participants and it will be divided in 3 phases: 1 minute of stable comfortable speed, 150 seconds of speed increments and 150 seconds of speed decrements. The randomization procedure for the time in between every speed variation will ensure that each speed level lasts between 5 and 15 seconds. Each verbal report given by the participants will be immediately recorded by the experimenter.

Obtaining a continuous report of the perceived treadmill speed and confronting it with the actual one will allow us to calculate an intra-subject correlation coefficient between perceived and actual speed, reflecting perceptive correspondence accuracy. This degree of correspondence may vary within a performance and therefore the minute by minute or protocol subphases accuracy dynamics will be also studied (see 'Data and statistical analysis').

[figure not shown]

Figure 9 Perceptive accuracy for imposed speed variations during treadmill walking: Task 1 illustration, wearables placement and Perception vs Performance plot graphic illustration (example pattern of imposed speed).  $\Delta_{min1-6}$  indicates that within-protocol variability in the intrasubject correlation will be studied for the different subphases of the protocol.

The intensity of perceived fatigue will be asked just before and immediately after the test using the VAS-F (see Figure 5). Furthermore, a short structured interview will follow including the following question: "On a scale from 0 to 100, how certain are you that you have been precise/accurate in detecting ongoing variations in your performance? Please mark your confidence level on the presented visual scale" (see Figure 7). This question is then followed by an open-ended question where the participant is asked to report on which sensory information he/she was relying to gauge performance variations and give the reports: "On which aspects of your motor performance where you paying attention to detect variations and decide to give a report during the task? Please list them here".

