### Task 2: Perceptive accuracy for imposed seat height variations during STS postural transitions

The participants will be tested on a motorized height-adaptable armless chair will allows us to test the perception of imposed sit-to-stand variations in a similar fashion to the treadmill protocol in Part B – Task 1.

A familiarization with the range of seat height, personalized accordingly to the length of the lower leg (see above, 'Range of experimentally-induced performance variations – Sit to stand'), will precede the start of the perceptive task.

Neutral instructions will be provided to the subject before starting the test, by reading the following script: "Start performing STS repetitions at the pace at which you are instructed by the examiner and try, to pay attention, each time, to the seat height. We want you to notice, evaluate and report the seat height to the experimenter relative to the visual scale on the screen: its starting position on the zero value represent your comfortable seat height, the maximum seat height from which I will ask you to stand up. The value of -100, instead, represents the most difficult sit-to-stand you may be asked to perform in the session: the lowest seat-height. Variations may occur at any point throughout the experiment, always within your personalized range. Sometimes it is possible that you will not feel any seat height variation at all. After every STS you will communicate the seat height level you perceived at that point in time, and your report will be recorded".

The seat will be positioned behind the subject at the baseline normalized seat-height (100% lower leg length). Before the start of the experimental perceptive task the participants will be ensured that the chair will always stay safely positioned behind them and that a person is also standing behind in an attentive state to ensure safety.

During the experimental perceptive task the participant will be guided to execute sit-to-stand transitions paced by the experimenter: during the stance phase (10 seconds) in between STS repetitions, the seat height will be modified starting from the baseline (comfortable seat-height= 120% lower leg length) with fixed decrements (of 5% lower leg length) but with randomized n. of repetitions (0, 1 or 2) in between. The seat-height lowering will continue down to the personalized lowest seat-height, stabilizing on that value before increasing toward the baseline height.

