In the **experimental Part B** within-subject correlations will be calculated between the imposed performance in motor tasks and the perception of its variations. These correlations will be examined separately for different phases of each trial to index perceptive accuracy. Fisher Z transformations (or other types of transformations eg. log transformation) will be applied to these correlations before further analysis, with results back-transformed for reporting. We will study it between and within groups using a mixed model ANOVA with time (protocol subphase) and group as factors to detect significant differences between PwMS and controls and its variations relative to the different subphases of the protocol. To investigate its interference with perceptive accuracy the difference between the subjective rate of fatigue (VAS-F) pre-post protocols will be included in the analysis as covariate. The correspondence between measured and reported dimensions of perceptive accuracy will be calculated as their absolute difference and compared between groups using an independent T test (or with its non-parametric equivalent).

Finally, for the accuracy outcomes derived from both experimental parts we will explore correlations, separated per group, to investigate the relationship between objectively measured perceptive accuracy and factors that potentially interfere with it (demographics, questionnaires and clinical assessments). Then, a regression analysis will be performed to assess the strength of these relationships and identify the most important explanatory factors or predictors.

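### Part B fixes the direction of change within each phase, so the per-phase correlation mostly measures a shared trend and can, though need not, imitate the hypothesised last-subphase deficit

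*Combined protocol and SAP*

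**What the plan says.** The treadmill task (Experimental design Part B, Task 1) lasts six minutes: 60 s at comfortable speed, 150 s of increments and 150 s of decrements. It uses "fixed increments (of 0,028m/s) but with randomized time in between every acceleration"; each level lasts 5 to 15 s. "the increase in speed will continue for 15 consecutive incremental steps", and the fall uses the same number of steps. The section says the protocol "will impose the absolute magnitude of speed changes (0,42 m/s) for all participants", but also that the rise continues "although never trespassing the participant's maximal speed". The participant is told that the scale starts at zero and reports the perceived level every 10 s on a 0 to +100 scale.

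The seat task (Part B, Task 2) has the same there-and-back form: "The seat-height lowering will continue down to the personalized lowest seat-height, stabilizing on that value before increasing toward the baseline height".

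Accuracy is the within-subject correlation of reported with imposed level. Data and statistical analysis adds: "These correlations will be examined separately for different phases of each trial to index perceptive accuracy". The correlations are Fisher z-transformed and enter a mixed ANOVA with subphase and group as factors and the pre-post change in VAS-F as covariate. The Part B hypotheses include: "PwMS will be less accurate than controls to a larger extend in the last subphase of the protocol". For Part B, the plan describes no detrending, error measure or variation of direction.

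**The concern.** Two things are at stake. First, if the imposed level within a phase is close to a line in time, reports that drift the right way correlate highly with it, whether or not the changes were felt. The index could then sit near its ceiling in both groups and hide a real difference.

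Second, the rise always comes first and starts from a known zero; the fall always comes second. A reporter whose perception is equally poor throughout can still score lower in the fall, because the reports must first reverse. If that kind of poor perception is commoner in people with MS, a group by subphase effect appears in the predicted direction although perception did not worsen during the protocol.

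**Working it through.** **The plan's own figures.** 15 × 0.028 = 0.42 m/s. 15 levels × 10 s average = 150 s. 60 + 150 + 150 = 360 s. These reproduce. Reports every 10 s give 150/10 = 15 per ramp. In the first 60 s the imposed level is constant, so no correlation exists there; the usable contrast is rise against fall.

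**Worked example by hand.** Take one permitted schedule, a step every 10 s. At report k = 1…15 the level is k in the rise and 15 − k in the fall. Consider a reporter who perceives every level perfectly but 40 s (four reports) late, with r = Sxy/√(Sxx·Syy) and Sxx = 280 in both phases.

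- Rise: reports 0, 0, 0, 0, 1, …, 11. Sxy = 242, Syy = 215.6, r = 242/√(280 × 215.6) = 0.985.
- Fall: reports 12, 13, 14, 15, 14, …, 4. Sxy = 204, Syy = 174.4, r = 204/√(280 × 174.4) = 0.923.
- Fisher z: 2.44 against 1.61.
- Mean absolute error: rise (1 + 2 + 3 + 12 × 4)/15 = 3.60 steps; fall (2 + 0 + 2 + 12 × 4)/15 = 3.47 steps.

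The deficit is the same throughout. The correlation drops in the fall; the error does not.

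**Simulation with randomised timing.** Inputs from the plan: 15 levels of 5–15 s summing to 150 s per ramp, a report every 10 s, Pearson r per phase. Assumptions: first step at 60 s, first decrement at 210 s, and all the reporter types. Noise SD is in steps of 0.028 m/s. Each row used 2,000 or 3,000 runs and gives the mean or median r.

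| Reporter | Rise | Fall |
|---|---|---|
| Straight line, no step felt, turns at peak, SD 1.5 | 0.94 | 0.95 |
| True tracker, SD 1.5 | 0.95 | 0.95 |
| Tracker, SD 2 | 0.917 | 0.921 |
| Tracker, SD 5 | 0.677 | 0.679 |
| Low gain (0.3 of true change), no noise | 1.000 | 1.000 |
| 20 s delay, no noise | 0.987 | 0.990 |
| 40 s delay, SD 1.5 | 0.92 | 0.88 |
| 50 s delay, SD 1.5 | 0.90 | 0.79 |
| Detection threshold 8 steps, SD 1 | 0.85 | 0.48 |
| Steady climb, never turns | 0.992 | −0.996 |
| Wandering from zero, no perception | +0.28 | −0.17 |

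**How much the trend-follower must know.** For a noise-free steady counter, fall-phase r is 0.990 if the turn comes 20 s late, 0.968 at 30 s, 0.917 at 40 s and 0.649 at 60 s. If the speed cap stops the rise at 10 steps, a counter turning at 210 s scores 0.914 and 0.935; at 6 steps, 0.707 and 0.766. In the seat task, with (120 − 80)/5 = 8 steps, the counter scores 0.987 and 0.986.

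**Effect on the planned test.** With 40 per group, a t-test on the rise-fall difference in Fisher z at two-sided 0.05 (400 runs, noise SD 2) rejected in the hypothesised direction in 20% of runs when delays were 10 s against 30 s, and in 5% for 10 s against 20 s. With no delay and noise SD 2 against 4 it was 2%, the chance level.

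**Alternative indices, same data.** In the simulation, mean absolute error stays level under a 40 s delay (3.46 rise, 3.55 fall, in steps) and under wandering (5.63, 5.59). Correlating successive changes separates the straight-line reporter (about 0.00) from the tracker (0.27 rise, 0.23 fall). However, a noiseless reporter only 5 s late scores about 0.02 and 0.06 on it, while keeping a level correlation of 0.99 in both phases.

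**The case against.** Participants are asked for the current level, not for individual steps, so correspondence of levels is a legitimate construct; detecting changes is the task of Part A. The hypothesis itself defines the last subphase as the return to comfortable levels, and the introduction expects prior beliefs to dominate perception in some people with MS. Missing the reversal or updating late may therefore be signal, not artefact. The instructions disclose neither direction nor turn, so a trend-follower scores well in the fall only by noticing or guessing the reversal. The delays that matter are long against a 10 s report interval. VAS-F change is a covariate, and the study is declared exploratory.

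Much of this stands. A missed turn is a real loss of accuracy on the return. But a uniform delay or threshold is not a last-phase deficit, and the correlation presents it as one. The covariate is one pre-post number per participant and task, so it cannot separate direction from elapsed time.

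A reader might infer that poor perceivers must score lower in the last phase by construction. The documents do not support that: noisy, low-gain and mildly delayed reporters score about the same in both phases. Nor does everyone receive an identical schedule, since step timing is randomised and the speed cap can shorten the ramp.

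**Conclusion.** The concern holds in a limited form. Direction, order and elapsed time coincide in both Part B tasks. For a full ramp, a reporter who feels no individual step but follows the trend, and turns within about 30 s of the reversal, scores about 0.9 or more, much like a true tracker. This weakens if the cap shortens the ramp substantially.

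The correlation falls mainly in the last phase under slow updating (about 40 s or more), a high detection threshold, a missed turn or wandering reports. It does not under purely noisy or low-gain perception. The schedule can therefore imitate the last-subphase hypothesis, without having to. How often it would do so depends on how participants actually report, which the documents cannot show; the reporter models, noise levels and delays above are assumptions. The point is worth settling before analysis, because a stated Part B hypothesis rests on this contrast.

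**What to change.** In the Part B paragraph of Data and statistical analysis:

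1. State that a group by subphase effect on the level correlation cannot by itself be read as an effect of time or fatigue, because direction, order and elapsed time coincide.
2. Add, per phase, the mean absolute difference between reported and imposed level, with the imposed level on the participant's own scale: for the treadmill, 100 × (speed − comfortable)/(maximal − comfortable), and the equivalent for the seat. Require the last-subphase hypothesis to be supported on this error as well as on the correlation.
3. If a change-based correlation is added, label it exploratory, since a 5 s reporting delay removes it.

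The scale anchors need one description each before step 2 can be computed. Maximal speed is tied to a 15 s stretch in one place and to the first minute of the walk test in another, and baseline seat height appears as both 100% and 120% of lower leg length. These passages must be reconciled.

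No new data are needed: a few lines of Matlab and the plan text. The downsides are one more outcome per phase, and an absolute error that also reflects gain and offset in scale use. The error measure does not separate trend-following from step perception either; that limit stays and should be reported. A missed turn still raises the error in the fall (holding at level 15 in the worked schedule gives (1 + … + 15)/15 = 8 steps), which is appropriate, since accuracy is then truly lower on the return.
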